Post-Authorisation Safety Study (PASS) Information

Acronym/Title	Study to Evaluate Physician Awareness and Knowledge of Safety and Safe Use Information for Androcur and Other Cyproterone Acetate Monotherapies in Europe: an Observational Post-Authorisation Joint Safety Study (Safe- CAM)	
Protocol version and date	v 2.0, 18 FEB 2021	
IMPACT study number	21490	
Study type / Study phase	Observational, post-approval Postmarket surveillance, Phase IV (Post-Market Clinical Follow-Up study) PASS Joint PASS: YES NO	
EU PAS register number	Study not yet registered	
Active substance	INN: Cyproterone; ATC code: G03HA01	
Medicinal product	Androcur (cyproterone) and its generics	
Product reference	BAY94-8367	
Procedure number	EMEA/H/A-31/1488	
Study Initiator and Funder	Bayer Pharma AG on behalf of a group of MAHs	

Research question and objectives	The primary objective of this study is to measure physician awareness and level of knowledge of the key safety information included in the revised summary of product characteristics (SmPC) and the Direct Healthcare Professional Communication (DHPC) for CPA monotherapy regarding the risk of meningioma. Specifically, the following information will be collected: • Investigate whether physicians have received and
	 reviewed the revised SmPC and DHPC Assess physicians' knowledge and understanding of key safety information pertaining to the following restrictions for the use of CPA due to the risk of meningioma. Specifically: The occurrence of meningiomas (single and multiple) in association with CPA monotherapy doses ≥ 25 mg/day
	 Restriction of use of CPA monotherapy 10 mg/50 mg in women when no results have been achieved at lower dose CPA-containing products or with other treatment options Restriction of use of high-dose CPA in men with sexual deviations when other interventions are not appropriate After clinical improvement with CPA monotherapy is achieved, treatment should be maintained with the lowest possible dose The risk of meningioma increases with increasing cumulative doses of CPA CPA is contraindicated in patients with a meningioma or a history of meningioma If a patient treated with CPA monotherapy is
	diagnosed with meningioma, treatment with all cyproterone-containing products must be permanently stopped Awareness of signs and symptoms of meningiomas
Country(-ies) of study	France, Germany, Poland, Spain, the Netherlands
Author	PPD PPD

ENCePP European Network of Centres in Pharmacoepidemiology and Pharmacovigilance

EU European Union

FDA Food and Drug Administration
GPP Good Publication Practice

GVP Good Pharmacovigilance Practice

ICH-GCP International Council for Harmonisation—Good Clinical Practice

IEC Independent Ethics Committee
INN International Nonproprietary Name

IRB Institutional Review Board
MAH Marketing Authorisation Holder
OQA Office of Quality Assurance
PAS Post-Authorisation Study

PASS Post-Authorisation Safety Study

PRAC Pharmacovigilance Risk Assessment Committee

PPD

Safe-CAM Safety of Cyproterone Acetate Monotherapy

SAP Statistical Analysis Plan

SmPC Summary of Product Characteristics

STROBE Strengthening the Reporting of Observational Studies in Epidemiology

3. Responsible parties

Bayer AG is the marketing authorisation holder of Androcur (cyproterone acetate) in the European Union (EU) and the study initiator and partial funder of the study. Other Marketing Authorisation Holders (MAH) of cyproterone acetate (CPA) monotherapy products are also funding the study. Bayer is responsible for fulfilling any obligations for reporting results to regulatory agencies. Bayer is collaborating with ppd an independent non-profit research organisation. PPD is responsible for the design, conduct, analysis, and reporting of the study. PPD a global research operations partner, is responsible for physician recruitment and data collection.

3.2 Collaborators/Committees

Contact details on the coordinating and/or principal investigators, co-investigators and other site personnel for each country and site participating in the study are listed in a stand-alone document (see Annex 1. List of stand-alone documents), which is available upon request.

Administrative changes of responsible persons and/or the composition of the committees will be documented by updating the respective lists, but do not require formal protocol amendments.

4. Abstract

Acronym/title	Study to Evaluate Physician Awareness and Knowledge of Safety and Safe Use Information for Androcur and Other Cyproterone Acetate Monotherapies in Europe: an Observational Post-Authorisation Joint Safety Study (Safe-CAM)	
Protocol version and date	v 2.0, 18 Feb 2021	
IMPACT study number	21490	
Study type / Study phase	Observational, post-approval	
	Postmarket surveillance, Phase IV (Post-Market Clinical Follow-Up study)	
	□ PASS □ Joint PASS: □ YES □ NO	
Author	PPD	
Rationale and background	As an outcome of an Article 31 referral for CPA monotherapy, Bayer has revised the summary of product characteristics (SmPC) and developed a DHPC to describe the risk of meningioma associated with the use of CPA. Bayer along with the other Marketing Authorisation Holders (MAHs) for CPA are conducting a joint observational cross-sectional survey to assess physicians' awareness and level of knowledge of the key safety information included in the revised	
	SmPC and the DHPC regarding risk of meningioma.	
Research question and objectives	The primary objective of this study is to measure physician awareness and level of knowledge of the key safety information included in the revised SmPC and the DHPC for CPA monotherapy regarding the risk of meningioma. Specifically, the following information will be collected:	

	Investigate whether physicians have received and reviewed	
	the revised SmPC and DHPC	
	• Assess physicians' knowledge and understanding of key safety information pertaining to the following restrictions for the use of CPA due to the risk of meningioma. Specifically:	
	 The occurrence of meningiomas (single and multiple) in association with CPA monotherapy doses ≥ 25 mg/day Restriction of use of CPA monotherapy 10 mg/50 mg in women when no results have been achieved at lower dose CPA-containing products or with other treatment options Restriction of use of high-dose CPA in men with sexual deviations when other interventions are not appropriate After clinical improvement with CPA monotherapy is achieved, treatment should be maintained with the lowest possible dose The risk of meningioma increases with increasing cumulative doses of CPA CPA is contraindicated in patients with a meningioma or a history of meningioma If a patient treated with CPA monotherapy is diagnosed with meningioma, treatment with all cyproterone-containing products must be permanently stopped Awareness of signs and symptoms of meningiomas 	
Study design	The study will be an observational, cross-sectional survey to assess knowledge and understanding among a diverse sample of physicians who have recently prescribed (e.g., within previous 12 months) CPA monotherapy in France, Germany, Poland, Spain, and the Netherlands. Physicians from a physician panel will be invited to complete a brief web-based questionnaire regarding their knowledge of the revised SmPC and DHPC.	
Population	Physicians eligible to participate will include dermatologists, endocrinologists, gynaecologists, general practitioners, urologists, oncologists (who treat prostate cancer), and psychiatrists involved in the treatment of hypersexuality/reduction of drive in sexual deviations who have prescribed CPA in the past 12 months and work in an office or hospital-based setting. Countries included are France, Germany, Poland, Spain, and the Netherlands.	

Variables	The physician questionnaire will assess physician knowledge of the key safety messages outlined in the revised SmPC and evaluate their receipt and understanding of the DHPC.	
Data sources	Data will be obtained through questionnaire responses from physicians enrolled in panels from targeted countries.	
Study size	The study will target the recruitment of a minimum of 600 participating physicians across the 5 countries. Specifically, we will target a minimum of 200 physicians in France and a minimum of 100 physicians each in Germany, Poland, the Netherlands, and Spain. In Poland and the Netherlands, the estimated patient exposure is low, and it may not be feasible to recruit 100 physicians in those countries within the study timeline. If this is the case, a minimum of 60 physicians will be targeted in Poland and the Netherlands and more physicians will be recruited among the other countries to ensure a total of at least 600 participating physicians.	
	The study will target recruitment based on the following parameters:	
	 Up to 30% of the total respondents in each country will be general practitioners 	
	• Up to 25% of the total respondents in each country will be urologists or oncologists with a minimum of 5 of each type (e.g., 10% urologists and 15% oncologists)	
	The remaining respondents in each country will be dermatologists, psychiatrists, gynaecologists, and endocrinologists, with a minimum of 5 physicians each for dermatologists, psychiatrists, and gynaecologists in each country. Given the high prescribing pattern of CPA monotherapy by gynaecologists in France, up to 40% of total respondents in France will be gynaecologists. Efforts will be made to recruit 5 endocrinologists in each country.	
Data analysis	Analyses will be descriptive in nature and no hypothesis testing will be performed. Tables displaying the frequency distribution of responses to each individual question will be created. Physician results will be stratified by country and other logical variables (e.g., practice setting, whether the physician received the DHPC). A detailed analysis plan that describes methods of analysis and presentation, including table shells, will be developed before data collection is initiated. In addition to a description of the analysis of the questionnaire data, the analysis plan will include a comparison of characteristics of participants	

	to the overall population of each specialty, based on available data, to gauge how representative the final sample is.	
Milestones	Registration in the EU PAS Register: before the start of data collection	
	• Ethical review (as required): before the start of data collection	
	• Distribution of revised SmPC and DHPC: estimated through May 2020	
	Start of data collection: Q3 2021	
	Analytical data set completely available: Q1 2022	
	• Final study report available: Q2 2022	

5. Amendments

None

6. Milestones

Table 1 presents planned milestones for the project. These milestones are based on a timely review and approval of the project. Administrative changes to milestones due to delays in study preparation and enrolment do not require amendments to the protocol. Revised study timelines and milestones which do not constitute a need for a formal protocol amendment are kept as stand-alone document (Annex 1) that is available upon request.

Table 1: Milestones

Milestone	Planned date ¹
Registration in the EU PAS Register	Before the start of data collection
Ethical review (as required)	Before the start of data collection
Start of data collection	Q3 2021
End of data collection	Q4 2021
Final report of study results	Q2 2022

EU PAS Register = European Union electronic Register of Post-Authorisation Studies.

¹ Planned dates are based on timely approval of the study protocol by EMA; delays in approval will impact these timelines.

7. Rationale and background

Cyproterone acetate (CPA) is a synthetic progesterone derivative with antiandrogenic properties and is available as monotherapy in dosages of 10 mg, 50 mg, and 100 mg for oral administration and 300 mg/3 mL in depot formulation for intramuscular administration in multiple European countries. The CPA monotherapy 10 mg and 50 mg strengths authorised indications are for moderate and severe signs of androgenisation in women (e.g., hirsutism, androgenetic alopecia, acne and seborrhoea), while the authorised indications for formulations of 50 mg and above and depot formulations are for reduction of sex drive in hypersexuality and sexual deviations in men and antiandrogen treatment in inoperable carcinoma of the prostate or palliative antiandrogenic treatment of prostate cancer. Approved indications for CPA monotherapy differ among the different strengths and among countries in which CPA monotherapy products are authorised.

A recent French pharmacoepidemiology study was conducted by Weill and colleagues (1) to estimate the number of cases of meningioma that are deemed attributable to prolonged exposure of CPA 50 mg and 100 mg in women between 2007 and 2015. A further overview was conducted by the French National Agency for Medicines and Health Products Safety to evaluate meningioma cases in which the use of CPA was reported. On 07 July 2019, the French National Agency for Medicines and Health Products Safety triggered a referral under Article 31 of Directive 2001/83/EC resulting from both of these resources, and requested that Pharmacovigilance Risk Assessment Committee (PRAC) assess the benefit-risk of CPA-containing products and to issue a recommendation on whether the relevant marketing authorisations should be maintained, varied, suspended, or revoked (2). In addition, the PRAC reviewed data from epidemiological studies, including the French Health Insurance (CNAM) study, postmarketing case reports, and data submitted by MAHs (2). The authors of the review concluded that while the absolute risk of meningioma in association with CPA use remains low, the risk increases with increasing cumulative doses. The PRAC noted that most cases occur after prolonged exposure to high doses of CPA (25 mg/day or higher), but cases of meningioma have also been identified after short-term exposure to high doses (cumulative dose > 12 g) of CPA (2). The PRAC concluded that the benefit-risk balance of CPA-containing products remains favourable.

The PRAC recommended that for all indications except prostate carcinoma, treatment with CPA should be restricted to situations where alternative treatments are unavailable or considered inappropriate, and that the lowest possible effective dose should be used. The PRAC also noted that available data do not indicate an increased risk of meningioma in association with low-dose combination products containing 2 mg or less of CPA. The PRAC further recommended updates to the product information of CPA-containing products to reflect current knowledge on the risk of meningioma. In addition, PRAC recommended the sponsors conduct a joint observational cross-sectional survey to assess physicians' awareness and level of knowledge of this risk.

In response to the PRAC recommendation to reflect current knowledge on the risk of meningioma, Bayer Pharma AG (Bayer) developed a Direct Healthcare Professional Communication (DHPC), in line with the content proposed by PRAC, associated with the risk minimisation plan for CPA monotherapy and has revised the summary of product characteristics (SmPC) to describe the risks associated with the use of CPA monotherapy. The DHPC and amendments to the relevant sections of the SmPC and package leaflet were adopted and distributed on a national level.

The PRAC has agreed that Bayer, along with the other MAHs for CPA monotherapies, conduct a joint observational cross-sectional survey to assess physicians' awareness and level of knowledge of

the key safety information included in the revised SmPC and the DHPC regarding risk of meningioma. The Co-ordination Group for Mutual Recognition and Decentralised Procedures for human use (CMDh) endorsed the DHPC.

This is an observational post-authorisation safety study (PASS) with the purpose of assessing physician knowledge and understanding of the key safety information included in the CPA educational material developed by Bayer. To meet the study objective, a physician questionnaire will be developed and administered to physicians prescribing CPA monotherapy to assess their knowledge and understanding of the key safety information in this material.

8. Research questions and objectives

The primary objective of this study is to measure physician awareness and level of knowledge of the key safety information included in the revised SmPC and the DHPC for CPA monotherapy regarding the risk of meningioma. Specifically, the following information will be collected:

- Investigate whether physicians have received and reviewed the revised SmPC and DHPC
- Assess physicians' knowledge and understanding of key safety information pertaining to the following restrictions for the use of CPA due to the risk of meningioma. Specifically:
 - The occurrence of meningiomas (single and multiple) in association with CPA monotherapy doses ≥ 25 mg/day
 - Restriction of use of CPA monotherapy 10 mg/50 mg in women when no results have been achieved at lower dose CPA-containing products or with other treatment options
 - Restriction of use of high-dose CPA in men with sexual deviations when other interventions are not appropriate
 - After clinical improvement with CPA monotherapy is achieved, treatment should be maintained with the lowest possible dose
 - The risk of meningioma increases with increasing cumulative doses of CPA
 - CPA is contraindicated in patients with a meningioma or a history of meningioma
 - If a patient treated with CPA monotherapy is diagnosed with meningioma, treatment with all cyproterone-containing products must be permanently stopped
 - Awareness of signs and symptoms of meningiomas

9. Research methods

9.1 Study design

The study will be an observational, cross-sectional survey to assess knowledge and understanding among a diverse sample of physicians who have recently prescribed (e.g., within the previous 12 months) CPA monotherapy.

Recruitment of the participating physicians will be performed by PPD and an internationally based data collection agency focused solely on health care research that maintains proprietary physician panels.

An invitation will be sent via e-mail to the selected sample of physicians, inviting them to participate and providing a link to a web-based questionnaire. To ensure physician eligibility, the web-based questionnaire will include a screening question to confirm the physician has prescribed CPA monotherapy in the past 12 months. Following consent, physicians will be asked to complete the questionnaire evaluating their knowledge and understanding of key safety information, as well as their receipt of the revised SmPC and the DHPC.

A cross-sectional survey approach was selected for this study because the main information on knowledge and understanding of the revised SmPC and the DHPC could be obtained only through direct interaction with physicians. The web-based format for completion of the consent form and questionnaire was chosen because of the efficiency of the method and the utility of the available electronic questionnaire tools (e.g., question branching logic and ability to display correct educational information at the conclusion of the questionnaire without allowing the participant to correct prior answers). Most physicians have convenient access to complete a web-based questionnaire, so the use of this technology is not thought to introduce respondent bias.

Participating physicians will be paid nominal incentives to compensate them for their time in completing the study questionnaire.

9.1.1 **Primary endpoint(s)**

This is a PASS survey study; no clinical endpoints will be assessed.

The questionnaire will collect information related to physician characteristics and experience with CPA monotherapy, as well as assess physicians' knowledge and understanding of risk and occurrence of meningiomas with CPA monotherapy, signs and symptoms of meningiomas, and treatment recommendations for CPA monotherapy. In addition, the questionnaire will include items to investigate physician receipt and use of the SmPC and DHPC for CPA monotherapy.

The primary endpoints to be assessed are the percentage of physicians responding correctly to each individual knowledge question.

9.2 Setting

This cross-sectional study will be conducted in five European countries: France, Germany, Poland, Spain, and the Netherlands. Five countries are included to provide some diversity in practice patterns and to observe physician knowledge in different settings, which will maximise the generalizability of the study. In addition, it is anticipated that the drug utilisation in these countries will be such that there will be a sufficient number of eligible physicians who have experience with CPA monotherapy to participate in the study. A brief informal feasibility assessment was performed in France, Germany, Poland, and Spain, and the results suggest that recruitment efforts will yield a sufficient number of eligible physicians to meet the targeted sample sizes in each country. The timing and sequence of study initiation in each country will be determined to allow for at least 6 months since the distribution of the SmPC and DHPC for CPA monotherapy.

9.2.1 Eligibility

Physicians eligible to participate will include dermatologists, endocrinologists, gynaecologists, general practitioners, urologists, oncologists (who treat prostate cancer), and psychiatrists involved

in the treatment of hypersexuality/reduction of drive in sexual deviations who have prescribed CPA monotherapy within past year and work in an office or hospital-based setting. The sampling frame will be constructed from a physician panel with the aim to select a sample that is generally representative of the types of physicians prescribing CPA monotherapy in each country.

9.2.1.1 Inclusion criteria

- 1. Licensed and practising dermatologist, endocrinologist, gynaecologist, general practitioners, urologist, oncologist (who treats prostate cancer), or psychiatrist involved in the treatment of hypersexuality/reduction of drive in sexual deviations
- 2. Prescribed CPA monotherapy to at least one patient in the past 12 months
- 3. Work in an office or hospital-based setting
- 4. Electronic acknowledgement of informed consent

9.2.2 Withdrawal

Each physician may discontinue participation at any time during the survey without giving a reason. If a physician wants to stop participating in the study, no further data will be collected.

9.2.3 Representativeness

The aim of physician recruitment is to obtain a sample generally representative of the physicians in the selected countries who potentially prescribe CPA monotherapy. Geographic location, specialty, and potentially other factors will be considered when selecting the sample in each country. The sample may include a simple random sample from the physician panels in each country. However, to achieve the appropriate distribution of prescribers in each specialty, we may adopt a sampling approach stratified by prescriber specialty in France and Spain. In smaller countries, the entire population of eligible physicians in the panel may be invited rather than a sample. To the extent possible, available information for nonrespondents or from national prescribing resources will be evaluated to assess if there are any differences (e.g., geography, specialty, sex, years in practice).

9.3 Variables

A questionnaire will be developed to elicit responses measuring physician knowledge and understanding of the key information included in the revised SmPC and DHPC for CPA monotherapy. This questionnaire will contain closed-ended questions (e.g., multiple choice, true/false) with no free-text response fields, eliciting responses measuring physician knowledge and understanding of the key information in the revised SmPC and DHPC for CPA monotherapy. The physician questionnaire will include items in the following content areas:

- Approved indications of CPA monotherapy
- Occurrence of meningiomas in association with CPA monotherapy
- Contraindications relevant to meningioma
- Signs and symptoms of meningioma
- Restriction of the indication to second-line treatment

- Approved dosing (i.e., treatment should be prescribed for the shortest possible time and with the lowest effective dose)
- Risk factors associated with meningioma (i.e., risk increases with increasing cumulative doses)

The questionnaire will also include the following items to investigate physician receipt and use of the DHPC and revised SmPC:

- Receipt and review of the DHPC and SmPC
- Estimated time between the physicians' review of the DHPC and SmPC and completion of the survey

In addition, the physician questionnaire will include queries on the following items to characterise the physicians and their practices:

- Physicians' practice setting
- Average number of CPA monotherapy prescriptions each month
- Years in practice
- Gender
- Age

Because approved indications and dosing vary by country, adaptations may be made to the questionnaire to ensure that it is specific and applicable to the country where it is being administered.

The questionnaire is anticipated to take 10 to 15 minutes to complete and will be administered in the local language for each country. The questionnaire will be administered electronically and programmed so that respondents will not be able to move backward in the survey to change their answers to previous questions.

The draft version of the questionnaire is included in Annex 3.

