9.9 Limitations of the research methods

As with all cross-sectional surveys that depend on health care professionals agreeing to participate, some limitations are inherent. Many methodologic and operational challenges are well recognised (7). Although the study is designed to select a diverse and generally representative sample of physicians who have recent experience with CPA monotherapy, there is no exhaustive list of all physicians who have prescribed or administered CPA monotherapy from which to draw a sample; hence, it is not possible to select a random sample of all physicians. Therefore, the study participants may not necessarily represent all physicians who have prescribed/administered CPA monotherapy. However, to the extent possible, information for respondents and nonrespondents will be evaluated to assess if there are any differences in available characteristics (e.g., geography, specialty, sex, years in practice).

In general, physician response rates for surveys have been somewhat low historically. In Germany, for post-authorisation safety studies, the German Medicinal Products Act (§ 67 Abs. 6 AMG, § 63f AMG) requires that physician participation in the study, as well as any associated compensation, be reported to the Federal Association of Panel Doctors, the Central Federal Association of the Health Insurance Funds, and the German Association of Private Health Insurance Funds. To meet this reporting requirement, physicians must provide their name and lifelong physician identification number as part of the survey. As a result, it is anticipated that the physician response to the survey may be particularly low in Germany.

Low response rates may result in a higher likelihood that participating physicians are not representative of all prescribing physicians. Thus, the resulting estimates of physician understanding about CPA monotherapy may be biased. If participants discontinue the survey because they do not know how to answer the knowledge questions, the frequency of substantial physician knowledge will be overestimated. Data will be collected to assess the number of physicians who begin but do not complete the questionnaire. This information can be used to help assess this potential bias. However, in our experience, almost all participants complete all items of the questionnaire.

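### The self-completed web questionnaire lets physicians look up answers before giving them; Section 9.1 rules out respondent bias on internet access alone and Section 9.9 does not name this upward bias

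*Protocol*

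**What the plan says.** Section 9.1 describes an e-mail to the selected physicians "inviting them to participate and providing a link to a web-based questionnaire". No interviewer is described for the main survey. Section 9.1.1 defines the outcome: "The primary endpoints to be assessed are the percentage of physicians responding correctly to each individual knowledge question".

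Two features bear on how answers are given. Section 9.3 has the questionnaire "programmed so that respondents will not be able to move backward in the survey to change their answers to previous questions". Section 9.1 lists, among the advantages of the electronic tool, the "ability to display correct educational information at the conclusion of the questionnaire without allowing the participant to correct prior answers". Section 9.3 also says "The questionnaire is anticipated to take 10 to 15 minutes to complete", but no time limit is stated.

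On bias from the mode, Section 9.1 says: "Most physicians have convenient access to complete a web-based questionnaire, so the use of this technology is not thought to introduce respondent bias". Section 9.9 returns to mode only to note that physicians without internet access cannot take part. The one route to overestimated knowledge that Section 9.9 names is drop-out: "If participants discontinue the survey because they do not know how to answer the knowledge questions, the frequency of substantial physician knowledge will be overestimated".

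Section 9.7.1 sets no a priori threshold but regards at least 60% correct per question as reassuring. Section 9.7 has the results read qualitatively for patterns across questions.

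**The concern.** Internet access affects who can respond. It says nothing about how an answer is produced once the questionnaire is open, so the conclusion in Section 9.1 does not follow from its premise.

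Blocking backward navigation and holding the correct information to the end both show that the authors want answers untouched by material seen during the session. The block covers material inside the questionnaire. It leaves the SmPC and DHPC, which are the very sources being tested, open to consultation before each answer.

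At stake is the meaning of the primary endpoint. The objective is physicians' awareness and knowledge, and Section 9.9 speaks of information understood and applied in practice. An answer read from the DHPC during the survey is not evidence of that. The error runs one way, in the same direction as the drop-out bias that Section 9.9 does acknowledge. The reported confidence intervals cannot reflect it because they describe sampling error only.

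**Working it through.** **Precision figures in the plan.** Table 2 gives exact (Clopper-Pearson) 95% limits. For n = 600 and 85% correct (510 of 600), beta quantiles return 81.9% to 87.8%, as printed. All 14 rows of the table reproduce to one decimal. The precision figures are therefore not in question. By the same method, 60% correct at n = 600 (360 of 600) gives 56.0% to 63.9%, about ±4 points.

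**Model for look-up.** Let k be the true share who know the answer and L the share of non-knowers who look it up and then answer correctly. Guessing is ignored. Then

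observed % correct = k + (1 − k) × L.

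The documents give neither k nor L. L is assumed at 10%, 20% and 30%. The values of k are 50% and 55%, assumed near the 60% benchmark, and 85%, the protocol's own illustration in Section 9.5.

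| True k | L = 10% | L = 20% | L = 30% |
|---|---|---|---|
| 50% | 55.0% | 60.0% | 65.0% |
| 55% | 59.5% | 64.0% | 68.5% |
| 85% | 86.5% | 88.0% | 89.5% |

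Example: 0.55 + 0.45 × 0.10 = 0.595.

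The look-up share that lifts an item to 60% is (0.60 − k)/(1 − k):
- k = 55%: 0.05/0.45 = 11.1%
- k = 50%: 0.10/0.50 = 20%
- k = 40%: 0.20/0.60 = 33.3%

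For items near 50% to 55%, the shift (4.5 to 15 points) is larger than the ±4 points of sampling error at n = 600. For a well-known item at 85% it is 1.5 to 4.5 points, against a half-width of about 3.

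**Would excluding look-up respondents repair the estimate?** Take k = 55% and suppose only non-knowers look up and all of them report it. Of 100 respondents, 45 × L are removed:
- L = 10%: 55/95.5 = 57.6%
- L = 20%: 55/91 = 60.4%
- L = 30%: 55/86.5 = 63.6%

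Exclusion still overstates 55%, because it removes non-knowers from the denominator. It is unbiased only if look-up is unrelated to knowledge.

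Counting reported look-up answers as not correct gives 55/100 = 55% in each case. If 10% of knowers also check a source (assumed), it gives 55 × 0.9 = 49.5%, below the truth. This version is therefore a lower bound when look-up is fully reported. If only half of it is reported at L = 20%, the figure is 64.0 − 4.5 = 59.5%, so under-reporting weakens the bound.

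**The case against.** The strongest reply is that the absence is shown for the protocol only. Annex 1 lists the questionnaire and the data management plan as stand-alone documents. Section 9.8.1 puts checks of accuracy, plausibility and validity in the latter, and Section 9.4 refers to introductory material that is pretested. An instruction to answer unaided, or item timing, could already be there. This stands, and the fix is conditional on it. It does not rescue the statement in Section 9.1 or the silence in Section 9.9. Annex 2 marks information bias as discussed in Section 9.9, yet that section deals with representativeness, response, drop-out and access.

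Look-up is also common to self-completed online surveys. The incentive is described as nominal compensation for time, and Section 9.1 says only that bias is not thought to arise. This is fair, and it is why the point concerns a limitation and a cheap safeguard, not the choice of mode.

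The survey does ask how long before completion the physician reviewed the DHPC and SmPC, and Section 9.7 plans stratification by time since review. That gives some view of very recent review, but it does not separate reading beforehand from looking up while answering.

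A reader might infer more than the documents support:
- **That physicians are told in advance their knowledge will be tested, and so prepare.** The invitation and consent texts are not available, so this cannot be said.
- **That look-up would carry the study past a success threshold.** Section 9.7.1 says no threshold is set, no hypothesis is tested, and one item passing 60% triggers nothing.
- **That every item is materially inflated.** At a true 85% there is little room to rise.

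**Conclusion.** The point holds as a correctable weakness. The protocol's stated safeguard does not address look-up, its no-bias statement rests on a premise about access, and its limitations section omits a bias whose expected direction is upward on the primary endpoint.

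The size cannot be estimated from the documents. Under the assumed look-up shares it could be material for items that only about half of physicians know, and it is small for items that most know. The illustration rests on three assumptions: the look-up shares, every look-up leading to a correct answer, and no guessing. The documents do not show that results will be inflated by any given amount, or that the study is invalid.

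**What to change.** 1. **Sections 9.1 and 9.3.** Unless the stand-alone questionnaire already does so, add an opening instruction to answer without consulting any source. Add one closed question, after the last knowledge item and before any educational screen, on whether a source was consulted. If these already exist, cite them in the protocol.
2. **Section 9.7.** Add a sensitivity table of percent correct per knowledge item, computed two ways: with respondents who report look-up excluded, and with their answers counted as not correct. Present the second as a lower bound subject to complete self-report. Do not rely on exclusion alone, for the reason shown above. Layout can be left to the SAP.
3. **Timestamps.** If recorded, report them descriptively. They should not define an exclusion, because a long session may be a clinical interruption.
4. **Section 9.1.** Limit the no-bias statement to access to the questionnaire.
5. **Section 9.9.** Name look-up as a limitation and state its upward direction.

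The cost is one instruction, one closed question and one extra set of tables. The downsides are a slightly longer survey and imperfect self-report. The instruction and the question must be in place before fielding, since the information cannot be recovered later.
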